12.1 General Considerations

All data will be summarized descriptively for the appropriate analysis sets defined below.

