12.5.2 Safety Analysis

Safety analyses will be based on the safety set. Safety and tolerability of artemether, lumefantrine and amodiaquine will be assessed by comparing the frequency (%) of adverse events and serious adverse events, with particular attention to abdominal pain, appetite perturbation and QT interval prolongation, using the Fisher's exact test. Safety data will be presented in tabular and/or graphical format and summarized descriptively. Any clinically relevant abnormalities or values of potential clinically concern will be described. Subjects will be analysed as treated.

An additional exploratory analysis evaluating independent renal markers against standard blood urea nitrogen/ creatinine levels will be conducted using appropriate statistical methods.

Adverse Events

All adverse event summaries will refer to treatment emergent adverse events, i.e. adverse

events that newly started or increased in intensity after the study drug administration. AE summaries will be generated for all AEs that occurred after study drug administration, until the end of the study.

12.6 Assessment of the relationship between pharmacokinetic parameters and ECG findings.

In addition to the results of the safety analysis, an exploratory analysis of the ECG data will be conducted. The ECG parameters will be compared with the PK properties of the drugs using appropriate statistical methods.

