2.4 SECONDARY ENDPOINTS

- a. Elimination clearance (CL/F), terminal elimination half-life (t_{1/2}) and apparent volume of distribution (V_d) of artemether, lumefantrine and amodiaquine and their metabolites when given alone and in combination.
- b. Safety and tolerability parameters, including adverse events, electrocardiographic changes, vital signs and biochemical assessments. •
- c. Pharmacogenetic polymorphisms in the case of unusual metabolizeStudy design

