2.5 GENERAL

This is an open-label pharmacokinetic study in 16 healthy Thai subjects. Subjects will be admitted in the inpatient ward and will be randomized to Artemether-lumefantrine followed by Amodiaquine or Amodiaquine followed Artemether-lumefantrine. There will be a washout period: > 6 weeks (after day 3) and then each of the participants will be given Artemether-lumefantrine + Amodiaquine. Thus, eEvery subject will have 1 screening and 3 admissions in the hospital.

All subjects will undergo screening assessments (visit 1). Screening assessments (visit 1) may be carried out over more than one day, provided that all required assessments are completed within the 14 days prior to visit 2. If the interval between screening (visit 1) and day -1 visit 2 is three days or less, the clinical laboratory screening test result and serum pregnancy test result can be used for enrolment evaluation on day -1 visit 2. In such cases, these tests would not need to be repeated at day1 visit 2

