3.5.2 Pharmacokinetic assessments

Individual pharmacokinetic parameters of artemether/dihydroartemisinin, lumefantrine/desbutyl-lumefantrine and amodiaquine/desethylamodiaquine will be calculated after each dose administration using a non-compartment approach.

Total exposure up to the last measured concentration (AUC_{LAST}) will be calculated using the linear trapezoidal method for ascending concentrations and the logarithmic trapezoidal method for descending concentrations. The terminal elimination half-life ($t_{1/2}$) will be estimated by the slope (λ_Z) of the best-fit log-linear regression of the observed concentrations in the terminal elimination phase. Drug exposure will be extrapolated from the last observed concentration to time infinity by C_{LAST}/λ_Z for each individual subject to compute total drug exposure (AUC_{∞}). Maximum concentration (C_{MAX}) and time to maximum concentration (T_{MAX}) will be taken directly from the observed data. Apparent oral elimination clearance (CL/F) and apparent volume of distribution (V/F) will be computed individually according to the equations below.

$$CL/F = \frac{Dose}{AUC_{\infty}} \quad V/F = \frac{t_{1/2} \times CL/F}{\ln 2}$$

The pharmacokinetic parameters will be summarised for each drug stratified by arm (i.e., when administered alone or in combination). Similarly, descriptive statistics will be summarised by arm. Ln-transformed pharmacokinetic exposure parameters (C_{MAX} , AUC_{LAST} and AUC_{∞}) will be evaluated to assess potential drug-drug interactions. No drug-drug interaction is assumed if the 90% confidence intervals of the ratio (combination/alone) of C_{MAX} , AUC_{LAST} and AUC_{∞} fall within 80% to 125% [10]. The 90% confidence intervals of the ratio (combination (COMB)/alone (ALONE)) will be calculated according to equation below.

$$Mean\ ratio\ (\%) = 100 \cdot e^{Parameter_{combination} - Parameter_{alone}}$$

where $Parameter_{combination}$ and $Parameter_{alone}$ are the least square mean of the natural logarithm of parameters derived for the combination and alone administration, respectively. The upper and lower boundary of the 90% confidence interval are calculated as follow:

$$90\% \ Confidence\ Interval = 100 \cdot e^{(Parameter_{combination} - Parameter_{alone}) \pm t_{0.95} \cdot SE_D}$$

STATISTICAL ANALYSIS PLAN FOR ALAQ STUDY

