3.5.3 Safety assessments

The incidence of AEs will be tabulated and reviewed for potential signals and clinical importance. The most prevalent AEs will be reported by group: (AL → AQ → AL + AQ) vs (AQ → AL → AL + AQ). Any Serious Adverse Events (SAEs) including any deaths will also be reported by group. Standard haematological parameters, serum chemistries, liver and renal function test results at screening and post-treatment will be summarised across the treatment groups. For the safety data such as adverse events, proportions will be compared using Fisher's exact test and a significance level of 5% where appropriate.

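### SAP 3.5.3 reports adverse events by randomised sequence, which cannot show a safety effect of co-administration; the tables should be by regimen

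*SAP*

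**What the plan says.** SAP 2.3 and Protocol 2.2 make the safety and tolerability of co-administered AL and AQ a secondary objective. SAP 2.4 gives the matching endpoint: "Safety and tolerability parameters, including adverse events, electrocardiographic changes, vital signs and biochemical assessments".

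SAP 3.5.3 holds the safety analysis:

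- AEs: "The most prevalent AEs will be reported by group", with the two groups written out as the two sequences. Serious AEs and deaths are also reported by group.
- Laboratory data: "Standard haematological parameters, serum chemistries, liver and renal function test results at screening and post-treatment will be summarised across the treatment groups". Whether these groups are sequences or regimens is not said.
- Proportions are compared with Fisher's exact test at 5% where appropriate. The groups compared are not named.
- Vital signs are not mentioned.

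SAP 2.5 describes the design: subjects are randomised to the order of AL and AQ, "and then each of the participants will be given Artemether-lumefantrine + Amodiaquine".

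Two other passages point to grouping by regimen. SAP 3.5.2 summarises the pharmacokinetic parameters "stratified by arm (i.e., when administered alone or in combination"). Protocol 12.5.2 says of safety that "Subjects will be analysed as treated".

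**The concern.** In this design randomisation sets only the order of the two single regimens. A table by sequence therefore compares two orders of the same treatments. The safety question is whether AL+AQ is tolerated worse than AQ alone or AL alone, and that comparison lies within each subject, across admissions.

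If the SAP is followed as written, the AE tables would look balanced whatever the combination does. A reader could take that balance as reassurance about co-administration, which it is not. The information needed is already collected, in the same 16 subjects under all three regimens.

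Heart rate is a useful example. Protocol 13.2 reports transient, symptom-free sinus bradycardia in 16 of 20 malaria patients treated with amodiaquine. Heart rate and blood pressure are measured supine and standing throughout visits 2 to 4.

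**Working it through.** The documents give no safety rate, effect size or power, so there is no planned figure to reproduce. The check has four steps.

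**1. What a table by sequence can show.** Inputs: 8 subjects per sequence (Protocol section 4, Table 1), and all three regimens given in both. Let r1, r2 and r3 be the chances of an event on AL, AQ and AL+AQ. With no carry-over or period effect, and periods independent for illustration, the chance that a subject has the event at least once is

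1 − (1 − r1)(1 − r2)(1 − r3)

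The order of the factors does not matter, so the two sequences have the same value. With assumed rates of 10%, 10% and 50% it is 1 − 0.9 × 0.9 × 0.5 = 59.5% in both columns. With AL+AQ at 80% it is 1 − 0.9 × 0.9 × 0.2 = 83.8% in both columns.

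**2. What Fisher's test by sequence can show.** With a common probability p in both columns, the chance of rejection is the sum of Bin(a; 8, p) × Bin(b; 8, p) over all tables a/8 v b/8 with two-sided p ≤ 0.05. Those tables are 0 v 5 to 8, 1 v 6 to 8, 2 v 7 to 8, 3 v 8, and their mirror images. The largest value is at p = 0.5, where each table has weight C(8,a) × C(8,b) / 65,536:

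- 0 v 5 to 8: 56 + 28 + 8 + 1 = 93
- 1 v 6 to 8: 224 + 64 + 8 = 296
- 2 v 7 to 8: 224 + 28 = 252
- 3 v 8: 56

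The total is 697. Doubled for the mirror images, 1,394 / 65,536 = 0.0213, or 2.1%. In the two scenarios of step 1 the chance is 1.9% and 0.2%: it falls as the harm grows.

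**3. What a comparison by regimen can show.** The same 16 subjects supply each regimen, so a paired test applies. Exact McNemar for AL+AQ v AQ, under the same assumed rates and independence between periods, has power of about 54% (AL+AQ 50%) and 98% (AL+AQ 80%). With all discordant pairs in one direction, five give p = 2 × 0.5^5 = 0.0625 and six give 2 × 0.5^6 = 0.031, so at least six are needed.

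For heart rate as a measurement, the 95% confidence interval half-width for the within-subject mean difference is t(0.975, 15) × SD / √16, with t = 2.131. The SD of the difference is an assumption:

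| Assumed SD (bpm) | Half-width (bpm), n = 16 |
|---|---|
| 5 | 2.7 |
| 6 | 3.2 |
| 8 | 4.3 |
| 10 | 5.3 |

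**4. Comparability of follow-up (Protocol 6.1.2).** After AL there are 5 scheduled follow-up visits: Days 4, 7, 14, 21 and 28. After AQ and after AL+AQ there are 7, adding Days 35 and 42. Abnormalities found only at a visit have two more chances of detection under AQ and AL+AQ than under AL.

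**The case against.** The strongest reply is that the protocol already covers this. Protocol 12.1 promises that "All data will be summarized descriptively for the appropriate analysis sets defined below". Section 12.5.2 compares the frequency of AEs and serious AEs, "with particular attention to abdominal pain, appetite perturbation and QT interval prolongation", and analyses subjects as treated. When everyone receives all three regimens, as treated can hardly mean anything but by regimen. Protocol 11.2 also makes abnormal heart rate and blood pressure reportable as AEs.

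Much of this stands. A reader might infer that neither document intends any comparison by regimen, or that vital signs will go unreported. The documents do not support either reading: Protocol 12.5.2 implies the first and 12.1 covers the second in general terms. The missing vital-sign and Holter tables in SAP 3.5.3 are mostly missing detail. What remains is that the SAP, the more specific document, spells out a different grouping for AEs, and that no AL+AQ v AQ or AL+AQ v AL contrast is named anywhere.

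A reader might also infer from the visit schedules that AEs on AL are observed for 14 days less. That does not follow. AEs are collected until the last follow-up of the study (Protocol 11.1 and Appendix 2), and AL is always followed by a washout of more than 6 weeks after Day 3. Only the scheduled visits differ.

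Finally, the 2.1% applies only if the Fisher test is run by sequence, which the SAP does not say. And AL+AQ is always the third period, so even the right contrast is confounded with period. That limits what a table by regimen can prove, but gives no reason to prefer one by sequence.

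**Conclusion.** The point holds for the grouping. As written, SAP 3.5.3 reports AEs and serious AEs in a way that cannot show an effect of co-administration. It departs from the as-treated rule of Protocol 12.5.2 and from the grouping that SAP 3.5.2 uses for pharmacokinetics. A Fisher test on that grouping would reject at most 2.1% of the time, assuming no carry-over or period effect.

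The correction should be made, but its reach is limited. The primary pharmacokinetic analysis is untouched, and with 16 subjects the safety comparison stays descriptive. The power and heart-rate figures rest on assumed event rates and SDs that the documents do not give.

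**What to change.** In SAP 3.5.3:

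1. Tabulate AEs, serious AEs and laboratory values by regimen (AL, AQ, AL+AQ). Assign each AE to the regimen most recently dosed.
2. For any test of AL+AQ v AQ or AL+AQ v AL, use exact McNemar in place of Fisher, because the same subjects contribute to both sides.
3. Summarise the vital signs by the same regimens, with the within-subject mean heart-rate difference and its 95% confidence interval. Name one summary per subject and regimen in advance, so that readings every 4 hours in two positions do not produce dozens of intervals.
4. Compare visit-detected events on AL+AQ and AL over the common visit schedule to Day 28.
5. State that AL+AQ is always the last period, so these contrasts are confounded with period.

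The cost is SAP wording and a few extra tables from data already collected. The drawback is a contrast that cannot be separated from period, which item 5 discloses.

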Amodiaguine by oral administration is absorbed rapidly, and then extensively metabolized to N-desethylamodiaquine (active metabolite) and 2-hydroxy-desethyl-amodiaquine by hepatic first-pass effect. C_{max} of amodiaguine in plasma, whole blood and packed cells is 32±3ng/ml, 60±10ng/ml and 42±6ng/ml respectively; Tmax of amodiaguine is 0.5±0.03h, 0.5±0.1h and $0.5\pm0.1h$ respectively; AUC₀₋₈ of amodiaguine in plasma, whole blood and packed cells is 99 ± 19 ng·ml⁻¹h, 148 ± 25 mJ⁻¹h and 167 ± 72 ng·ml⁻¹h respectively. Cmax of desethylamodiaguine in plasma, whole blood and packed cells is 181±26ng/ml (19 fold higher than those of the parent drug), 561±70ng/ml and 561±143ng/ml respectively; Tmax for desethylamodiaguine is 3.4±0.8h, 2.2±0.5h and 3.6±1.1h respectively; and AUC0-24 for desethylamodiaquine in plasma, whole blood and packed cells is 2304±37ng·ml⁻¹h, 6811±752ng·ml⁻¹h and 5713±1269ng·ml⁻¹h respectively (whole blood AUC was higher than plasma AUC, P<0.001). The trial of ¹⁴C-labelled amodiaquine administered orally to Wistar rats showed that amodiaquine can be distributed widely in body with the main organs of accumulation being kidney, liver, bone marrow and spleen. Amodiaquine is not observed in plasma 8 hours after administration, whereas the concentration of desethylamodiaquine in plasma at 96h is 29 ± 8 ml⁻¹. The half-life of amodiaguine in plasma is 5.2 ± 1.7 h, and elimination half-life ($\beta_{t1/2}$) of desethylamodiaquine in plasma is 9-31 days. The bioavailability of amodiaquine is decreased due to first-pass hepatic metabolism. The plasma protein binding rate of amodiaguine and desethylamodiaguine is greater than 90%. The T_{max} of amodiaguine taken orally by patients with falciparum malaria is 1.75h, distinctly longer than the T_{max} of healthy volunteers (18).

Potential interactions through hepatic metabolism

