5. STUDY POPULATION

5.1. Number of Subjects

This study will enroll 16 healthy subjects both male and female, aged 18-60 years, at the pharmacokinetic unit Faculty of Tropical Medicine, Mahidol University. Subjects will be healthy HIV-1, hepatitis B and C uninfected individuals who comprehend the purpose of the study and have provided written consent. All subjects will undergo screening assessments (visit 1). Screening assessments (visit 1) may be carried out over more than one day, provided that all required assessments are completed within the 14 days prior to visit 2. If the interval between screening (visit 1) and day -1 visit 2 is three days or less, the clinical laboratory screening test result and serum pregnancy test result can be used for enrolment evaluation on day -1 visit 2. In such cases, these tests would not need to be repeated at day-1 visit 2.

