- 11. Subjects who have a history of allergy to the study drug or drugs of this class, or a history of drug or other allergy that, in the opinion of the investigator, contraindicates participation in the trial. In addition, if heparin is used during pharmacokinetic sampling, subjects with a history of sensitivity to heparin or heparin-induced thrombocytopenia should not be enrolled.
- 12. Lack of suitability for participation in this study, including but not limited to, unstable medical conditions, systemic disease manifested by tendency to granulocytopenia e.g. rheumatoid arthritis and lupus erythematosus that in the opinion of the investigator would compromise their participation in the trial.

- 13. AST or ALT >1.5 times the upper limit of normal (ULN)
- 14. Subjects with history of renal disease, hepatic disease, and/or cholecystectomy
- 15. Abnormal methemoglobin level (more than 3 mg/dL).
- 16. History of antimalarial drugs use including but not limited to mefloquine, chloroquine, primaquine, artesunate, piperaquine and pyronaridine treatment within 6 months.
- 17. Subject who have received quinacrine in last 30 days.
- 18. Subject has been included in other clinical trials in last 6 months.

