2.3 SECONDARY OBJECTIVES

- a. To characterize the pharmacokinetic properties of artemether-lumefantrine and amodiaquine when given alone and in combination.
- b. To evaluate the safety and tolerability of co-administered artemether-lumefantrine and amodiaquine. Protocol version 6.0 dated 22 June 2022 10 of 42.
- c. To investigate pharmacogenetic polymorphisms affecting drug levels of artemetherlumefantrine and amodiaquine and their metabolites.

STATISTICAL ANALYSIS PLAN FOR ALAQ STUDY

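### SAP 3.5.3 plans no laboratory summary by regimen and visit and names only screening as reference, so it does not describe AL+AQ safety against each drug alone

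*SAP*

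**What the plan says.** SAP 2.3 lists as a secondary objective "To evaluate the safety and tolerability of co-administered artemether-lumefantrine and amodiaquine". SAP 3.5.3 is the only SAP text on how laboratory data are analysed.

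- **Adverse events:** "The most prevalent AEs will be reported by group", and the two groups are then spelled out as the two randomised sequences.
- **Laboratory data:** "Standard haematological parameters, serum chemistries, liver and renal function test results at screening and post-treatment will be summarised across the treatment groups". No regimen, visit, Day -1 reference or within-subject contrast is named.
- **Test:** Fisher's exact test for proportions at 5%, where appropriate.

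SAP Table 1 (baseline) also has the two sequences as its columns. The SAP's term for regimen appears only for pharmacokinetics (3.5.2), where parameters are "stratified by arm (i.e., when administered alone or in combination".

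Protocol 6.3.5 and Appendix 2 (note 5) show that the data exist. A white cell count with differential and a chemistry panel are drawn on Day -1 and Day 3 of every admission and weekly in follow-up. The one exception is visit 2: if screening was three days or less before Day -1, "these tests would not need to be repeated at day-1 visit 2".

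**The concern.** Every subject receives AL, AQ and AL+AQ; only the order of the first two differs. A summary by sequence pools or mixes the regimens and cannot show what the combination adds to either drug alone, which is what the secondary objective asks.

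The reference point raises a second question. Screening is a defensible drug-free value for everyone. Used alone, however, it does not separate a change arising in the AL+AQ period from a shift already present when the subject was admitted for visit 4.

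What is at stake is description, not protection. Moderate shifts in counts or chemistry under AL+AQ relative to AQ would go unreported although the data are in hand. Neutrophils are a sensible variable to include: amodiaquine's listed risks (Protocol 13.2) include agranulocytosis, and exclusion 12 in Protocol 5.3 gives "systemic disease manifested by tendency to granulocytopenia" as an example of unsuitability.

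**Working it through.** The documents state no figure on this point, so there is none to reproduce. Inputs are from the documents unless marked as assumed.

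**1. Sequence contrast.** Let the falls in a count be a (AL), q (AQ) and q + d (AL+AQ), with no order effects. The mean over three periods is (a + q + q + d)/3 in both sequences, so the expected difference is 0 for every d.

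- *Simulation, 8 v 8.* Assumed: a = 0, q = 0.5, between-subject SD 1.0 and within-subject SD 0.7, all x10^3/uL. For d = 0, 0.5 and 1.0 the sequence contrast averaged -0.001, -0.003 and -0.002. The within-subject AL+AQ minus AQ contrast averaged 0.001, -0.501 and -0.998.
- *Events.* Assumed risks: AL 2%, AQ 5%, and AL+AQ 5%, 30% or 60%. The any-event risk is 1 - 0.98 x 0.95 x (1 - p) = 0.116, 0.348 or 0.628, the same in both sequences. Fisher's test between sequences would reject in 0.07%, 1.6% and 1.7% of trials.

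A by-visit table inside the sequence columns would separate the regimens. The SAP does not state one, and it would leave 8 subjects per column.

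**2. Age of the screening reference.** SAP 2.5: "There will be a washout period: > 6 weeks (after day 3". From visit 2 Day 0 to visit 4 Day 0 is more than 2 x (3 + 42) = 90 days, and screening is earlier still.

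**3. Residual metabolite at visit 4 Day -1, minimum washout.** Protocol 1 gives the elimination half-life: "desethylamodiaquine in plasma is 9-31 days". The share remaining is 2^(-gap/half-life), treating the terminal phase as a single exponential from the last dose.

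- *Group A (AQ second).* Last dose at 60 h = Day 2.5; earliest readmission Day 3 + 42 = Day 45; gap 42.5 d. 2^(-42.5/9) = 3.8%; 2^(-42.5/31) = 38.7%. If Day 45 is the dosing day, the gap to Day -1 is 41.5 d, giving 4.1% and 39.5%.
- *Group B (AQ first).* One more period of at least 45 d; gap about 87.5 d. 2^(-87.5/9) = 0.12%; 2^(-87.5/31) = 14.1%.

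Day -1 is therefore not guaranteed drug-free, mainly in Group A. This is the reason to show both references.

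**4. How the two references relate.** Write C and Q for the AL+AQ and AQ values at a matched visit, and C0 and Q0 for their Day -1 values. Referenced to screening, the paired difference is (C - S) - (Q - S) = C - Q. Referenced to Day -1, it is (C - Q) - (C0 - Q0). The two differ exactly by the shift between the two Day -1 values.

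**5. Precision of the paired difference.** The 95% half-width in units of its SD is t(0.975, n-1)/sqrt(n). The last column assumes an SD of 0.6 to 1.2 x10^3/uL for a neutrophil difference.

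| n | Half-width (SD) | Half-width (x10^3/uL) |
|---|---|---|
| 16 | 2.131/4 = 0.53 | 0.32-0.64 |
| 12 | 2.201/3.464 = 0.64 | 0.38-0.76 |
| 8 (one sequence) | 2.365/2.828 = 0.84 | 0.50-1.00 |

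**6. Number of draws.** Post-dose laboratory draws for AL are on Days 3, 7, 14, 21 and 28 (5). AQ and AL+AQ add Days 35 and 42 (7). The expected minimum of independent normal draws is -1.163 SD for 5 and -1.352 SD for 7. A lowest value is thus below a single Day -1 value by chance alone, and 0.19 SD further below with 7 draws than with 5.

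**The case against.** **The text may already mean regimens.** SAP 3.5.3 uses one term for adverse events and a different one, *treatment groups*, for laboratory data. Protocol 12.5.2 analyses subjects as treated, and Protocol 12 and 12.3 use group in a regimen-like sense. This stands in part. A reader might infer that laboratory analysis by sequence is settled; the documents support it only as the most natural reading. The as-treated rule permits a by-regimen table without specifying one, and the missing per-period reference remains either way.

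**Table 1 may be a period reference.** Its title places the baseline values at crossover, and it lists white cells and neutrophils. It is nevertheless one table by sequence, with no statement that it is repeated for each period, and it is not a change analysis.

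**Neutrophils are not a named focus.** Protocol 12.5.2 singles out abdominal pain, appetite and QT prolongation, and Protocol 13.2 ties agranulocytosis to long-term use. This stands, so the remedy covers haematology and chemistry generally, with absolute neutrophil count as one variable.

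**Baseline shifts are bounded.** Protocol 10.3 requires blood counts in the normal range before the next round. This stands: for counts, only shifts within that range are in question.

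**No analysis isolates the combination.** AL+AQ is always last. This stands, and limits the remedy to description.

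**Conclusion.** The concern holds as a minor point. Adverse events are explicitly tabulated by sequence, laboratory data most naturally are too, and screening is the only reference named. Neither layout describes AL+AQ against AQ or AL, although the secondary objective asks for it and the data are collected. If *treatment groups* means regimens, only the missing per-period reference is left.

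Three stronger inferences are not supported.

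- *That changes from Day -1 and from screening bracket the true effect.* That needs a count effect tracking residual drug, with no drift over more than 90 days and no noise. The documents give no basis for this.
- *That regimen columns would isolate the added effect of the combination.* Regimen, period and carry-over stay confounded.
- *That subjects are at risk.* Abnormal results are reported as adverse events (Protocol 11.2) and graded by CTCAE (11.4.1), and the normal-count gate applies (10.3). No case of agranulocytosis is expected in 16 subjects on 3-day courses.

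The zero sequence contrast assumes no order effects. The count SDs, event risks and single-exponential decay are assumptions; the 90-day gap and the half-widths in SD units are arithmetic.

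**What to change.** In SAP 3.5.3:

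1. Summarise haematology and chemistry, including absolute neutrophil count (white cells x neutrophil fraction), by regimen received and scheduled visit.
2. Give change from that period's Day -1, or from the substituted screening value where visit 2 Day -1 tests were waived. Show change from screening alongside, because desethylamodiaquine may persist at visit 4 Day -1.
3. Give the within-subject AL+AQ minus AQ difference at matched visits with its 95% CI. For any comparison with AL, use Days 3 to 28 only.
4. Present this descriptively, and state that AL+AQ is always last, so regimen, period and carry-over cannot be separated.
5. A lowest-count analysis is optional. If used, restrict it to the AL+AQ minus AQ difference over the same draw days, where the downward bias of a minimum largely cancels.

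The cost is one extra table and one derived variable, with no new sampling. It can be done before database lock.
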